#### 13.2.2.3. Disease Response Evaluable Set

All subjects who received any amount of ELI-002 vaccine who have positive MRD at baseline, and either:

1. Have at least 1 available post-baseline MRD assessment, or
2. Have experienced an RFS event (recurrence or death).

This population will be used for supportive analysis of biomarker clearance/reduction and duration of biomarker clearance/reduction.

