## 14.0 CHANGES TO PLANNED ANALYSIS FROM STUDY PROTOCOL

The protocol has indicated that statistical testing and confidence intervals would be computed for the efficacy analyses; however, since the sample sizes are small and efficacy data from this trial are exploratory and not powered to elicit statistically significant treatment effects, no formal statistical testing will be computed except for RFS and OS endpoints. ctDNA and Immunogenicity analyses are beyond the scope of this document and are specified in a separate addendum which is attached here as an appendix.

Additional exposure outcomes namely Dose Intensity (DI) and Relative Dose Intensity (RDI) not mentioned in the protocol will be summarized for better clarity on the treatment exposure.

The protocol has requested that summary statistics be presented for patient reported outcomes, however, due to the early termination of the long term follow up of the study, only by-subject listing will also be provided for these endpoints.

The protocol has requested the use of the Disease Response Evaluable Set population, however, as no outputs in the SAP/shells are based on this set, it was dropped from the SAP.

**Final Analysis  
Statistical Analysis Plan (SAP)**

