### **1.5. Population Definitions**

The following patient populations will be evaluated and used for presentation and analysis of the immunogenicity or ctDNA biomarker data:

- Immunogenicity Population: All patients who receive any amount of study treatment and contribute any immunogenicity data.
- ctDNA Population: All patients who receive any amount of study treatment and contribute any ctDNA data.

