## 2.2. ctDNA

ctDNA response is defined as the absence or reduction of circulating tumor DNA post-baseline. Analysis of ctDNA will be based on results from two laboratories and will be performed separately.

Duration of response is defined as the time in weeks from reduction until the date of increase or presence of ctDNA.

Any patient with detectable ctDNA at baseline whose post-baseline result is less than the baseline value or undetectable will be considered a responder. The number and percentage of responders will be reported.

Doubling will be calculated as the number of weeks between visits where ctDNA first doubles.

Doubling time and response will be based on the tumor molecules per mL (MTM/mL) and Variant Allele Frequency (VAF).

ctDNA levels over time will be summarized using descriptive statistics.

Data listings will present ctDNA values (VAF and MTM/mL) over time, ctDNA response, and duration of response, and time until doubling of ctDNA.

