(1) response is defined as decrease from baseline or undetectable value. (2) Duration is calculated as the date of the first response until the date where the ctDNA is detectable or greater than baseline value. (3) Doubling time is the time until the ctDNA has increase 2-fold from nadir.

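### The addendum's ctDNA response rate has no stated denominator: its population admits subjects whom the responder rule excludes, and two other wordings of response could count them as successes

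*SAP*

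**What the plan says.** The addendum describes ctDNA response three times.

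- The responder sentence in 2.2: "Any patient with detectable ctDNA at baseline whose post-baseline result is less than the baseline value or undetectable will be considered a responder".
- The opening sentence of 2.2: "ctDNA response is defined as the absence or reduction of circulating tumor DNA post-baseline".
- Footnote 1 of Listing 7: "response is defined as decrease from baseline or undetectable value".

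Only the responder sentence requires detectable ctDNA at baseline. Addendum 1.6 takes the ctDNA baseline from Visit 3, or from Visit 2 if Visit 3 is missing.

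On reporting, 2.2 says "The number and percentage of responders will be reported". Table 7 is titled for the population that addendum 1.5 defines as "All patients who receive any amount of study treatment and contribute any ctDNA data". Its response-rate row sits under cohort column headings with an N and has no footnote naming a denominator. Other rows of Table 7 do have footnotes saying what their N counts, and the response rows of addendum Table 1 state their denominator.

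Section 2.2 also analyses the two laboratories' results separately. Protocol 6.1.5 says that one diagnostic is used for each subject's enrolment.

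**The concern.** A response percentage needs a numerator and a denominator drawn from the same people. Here the rule restricts who can succeed, and the table's population does not restrict who is counted.

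Baseline-undetectable subjects are foreseen. Protocol inclusion criterion 4 admits subjects on rising or elevated serum markers as alternatives to a positive ctDNA test. The secondary endpoint (protocol 6.2.2, SAP 9.1.2) provides a serum-marker fallback when ctDNA is not detectable at baseline. The schedule of assessments draws ctDNA from everyone at Visit 3 and at set later visits, so these subjects contribute ctDNA data and enter the ctDNA Population.

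Assessing ctDNA reduction is the first objective in addendum 1.1. Protocol 4.6.5 treats biomarker reduction as preliminary proof of concept and looks for dose response in pharmacodynamic activity. SAP 13.1 puts emphasis on comparison with the lowest dose and says that the efficacy summaries are to inform later studies. A cohort rate that depends on how many subjects were undetectable at baseline can look like a dose difference, in either direction.

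**Working it through.** **No figure to reproduce.** The plan states no ctDNA response rate, power or denominator. SAP 10.0 plans about 18 subjects, 3 to 6 in each of three cohorts, without a power calculation.

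**Notation.** N is the number in the ctDNA Population, s the number undetectable at baseline, f = s/N, and r the response proportion among the N − s with detectable baseline ctDNA. The documents give neither s nor r, so the values below are assumptions.

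**Formulas.**

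- Responder sentence, denominator N: rate = r(N − s)/N = r(1 − f); ceiling = 1 − f.
- Opening sentence or Listing 7 footnote, denominator N, all s staying undetectable and counted as responders: rate = [r(N − s) + s]/N; floor = s/N.
- Denominator restricted to detectable baseline: rate = r; ceiling 100%.

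**Dilution when r = 60%, denominator N.**

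| Assumed f | Ceiling 1 − f | Reported rate 0.60 × (1 − f) |
|---|---|---|
| 20% | 80% | 48% |
| 30% | 70% | 42% |
| 40% | 60% | 36% |

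**One or two subjects in a cohort.** In a cohort of 3, one undetectable subject lowers the ceiling to 2/3 = 66.7%, a drop of 33 points. In a cohort of 6, one lowers it to 5/6 = 83.3%, a drop of 17 points, and two lower it to 4/6 = 66.7%.

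**Same data, three results.** Assume N = 18, s = 6 and 9 responders among the 12 with detectable baseline ctDNA (Clopper-Pearson 95% intervals).

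| Reading | Rate | 95% CI |
|---|---|---|
| Detectable baseline in numerator and denominator | 9/12 = 75.0% | 42.8 to 94.5 |
| Responder sentence over all 18 | 9/18 = 50.0% | 26.0 to 74.0 |
| Absence counts, all 6 stay undetectable | (9 + 6)/18 = 83.3% | 58.6 to 96.4 |

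If no detectable subject responds (r = 0), the third reading still gives 6/18 = 33.3%.

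**Case mix read as dose.** Take two cohorts of 6 with the same r = 1/2. With s = 0 the rate is 3/6 = 50.0%. With s = 2, four subjects are at risk and two respond: 2/6 = 33.3% over the column N, or (2 + 2)/6 = 66.7% if absence counts. Restricted to detectable baseline, both cohorts give 50.0% (3/6 and 2/4).

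**By assay.** If an assay-specific percentage were also taken over the whole cohort N, subjects not tested with that assay would lower it further. The plan does not say which N those rows use.

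**The case against.** The strongest reply is that the cap is inferred. Nothing says that the percentage is taken over the column N, and the opening condition of the responder sentence could be read as defining who is at risk. Footnote 2 of Table 7 counts only patients with detectable ctDNA, and the shell already has rows for the number undetectable, including at baseline. The addendum is descriptive, and Listing 7 shows each patient's results. This stands in part: the certain defect is an unstated denominator with conflicting definitions, and the downward bias follows only on the column-N reading. But footnote 2 belongs to the concentration rows, and a descriptive percentage has no later test or model to correct it.

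Several stronger readings are tempting, and the documents do not support them.

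- **That case mix, and not ELI-002, determines the rate.** Only the ceiling depends on f; below it, r(1 − f) moves with the effect.
- **That the bias must be downward.** The two wordings without a baseline condition can reverse it.
- **That serum-marker entry equals undetectable baseline.** The routes in criterion 4 are alternatives, so a subject qualifying on a serum marker may also have detectable ctDNA, and one positive at screening may be undetectable at Visit 3. Where the plasma RAS assay establishes the mutation, the same sample informs ctDNA positivity (protocol 6.1.5.1.2), so subjects undetectable at screening come essentially through the tumor-informed route.
- **That dropping the Disease Response Evaluable Set caused the problem.** Protocol 13.2.2.3 defined it as "All subjects who received any amount of ELI-002 vaccine who have positive MRD at baseline, and either" at least one post-baseline MRD assessment or an RFS event. SAP 14.0 explains that "as no outputs in the SAP/shells are based on this set, it was dropped from the SAP". Protocol section 13 lets serum markers define MRD, so the set could still have included subjects with undetectable ctDNA.
- **That the secondary endpoint is capped.** It has the serum-marker fallback, and SAP Table 8 selects the best result among ctDNA and the serum markers.

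**Conclusion.** The point holds for the addendum's ctDNA response rate and nothing wider. The numerator rule in 2.2 and the population of Table 7 do not match, the row has no stated denominator, and two further wordings of response conflict with the rule.

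On the column-N reading, a true 60% would be reported as 48% to 36% if 20% to 40% of subjects were undetectable at baseline. If absence alone counts, the rate is inflated and can be well above zero with no responders among those at risk. With 3 to 6 subjects per cohort, one such subject moves the ceiling by 17 to 33 points, so differences between cohorts can partly reflect case mix.

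The size rests on assumed values of f and r. If every treated subject had detectable ctDNA at baseline, the dilution and inflation from this source would vanish. The gap in definition is there whatever f turns out to be. It should be closed before the final tables are run.

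**What to change.** 1. Use one responder definition in addendum 2.2, Table 7 and Listing 7: detectable ctDNA at baseline, followed by a lower or undetectable post-baseline result.
2. Add a denominator footnote to the response-rate row of Table 7: treated subjects with detectable baseline ctDNA, and for by-assay rows those tested with that assay.
3. Count missing post-baseline results as non-response, in line with protocol 13.3.3.2. This requires the denominator to be treated subjects with detectable baseline ctDNA, whether or not a later sample exists.
4. Show the number undetectable at baseline beside the rate, by cohort.

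The cost is one agreed sentence, one footnote and one programming flag, with no new data. The downside is smaller denominators and wider intervals in cohorts that are already small.

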## 10. TIMING OF TRIAL PROCEDURES

Home Health Visits: Based on assessment of risk, and to ensure subject safety and minimize risks to trial integrity, off-site study visits can be performed in the event a study participant cannot attend an on-site visit during the COVID-19 crisis [[Food and Drug Guidance, 2020](#)]. The procedures that cannot be performed during a home health visit include:

- CT/MRI scans
- First ELI-002 dose administration (Visit 3, Day 57); this must occur on-site as per Section [10.2](#).
- Leukapheresis (Visit 2, Visit 9)

The informed consent form will describe the availability of home health visits if applicable at the clinical site.

The subject will be invited to continue future study visits on-site per protocol, as soon as local and federal Covid-19 regulations allow.

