**Table 1-1 Collection of Immunogenicity and ctDNA Samples**

Visit	Week	Immunogenicity	ctDNA
2	Baseline	X (Baseline)	X
3 (First dose)	0		X (Baseline)
4	1		
5	2	X	
6	3		X
7	5	X	
9	9	X	
11	17	X	X
12	20		X
14	22	X	
16	25	X	X
17	29		X
18	37		X
19	49		X
20	61		X
21	73		X
22	85		X
23	97		X
24	105		X

Visits labeled "unscheduled", or the equivalent may be collected,

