### **1.6. Baseline Definitions**

For all analyses, baseline will be defined as the most recent measurement prior to the first administration of study drug. For immunogenicity analyses, this will be the sample collected on Visit 2. For ctDNA, this will be the sample collected at Visit 3. If results are missing at Visit 3 but available for Visit 2, Visit 2 results may be used as baseline.

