DATE: HH:MM/DDMMYY

Protocol ELI-002-001                      Elicio Therapeutics, Inc.                      Confidential                      Page 1 of x

Table 7  
 Summary and Change from Baseline for ctDNA (ctDNA  
 Population)

Baseline	Baseline (1)	Cohort 1 (N=xx)	Cohort 1 (N=xx)	Cohort 1 (N=xx)
		N (2)	xx	--
		Mean (SD)	xx.x (xx.xx)	
		Median Min,	xx.xx xx.x	
		Max	xx.x	
		N Undetectable (3)	xx.x, xx.x xx	
		<repeat for remaining visits with at least 3 subjects		
Visit 6		N (2)	xx	xx
		Mean (SD)	xx.x (xx.xx)	xx.x (xx.xx)
		Fold Change Mean	xx.xx	xx.xx
		Fold Shange SD- SD	xx.x	xx.x
		Median	xx.x	xx.x
		Min, Max	xx.x, xx.x	xx.x, xx.x
		N Undetectable (3)	xx	xx
Doubling Time	N(4)	Mean (SD)		
		Median		
		Min, Max		
Clearance Duration (weeks)	N(5)	Mean (SD)		
		Median		
		Min, Max		
Response Rate	n%			

[1] Baseline is based on Visit 3 result or Visit 2 if Visit 3 is missing  
 [2] N reflects the number of patients with detectable concentrations of ctDNA .

[3] Number of subjects with results below the limit of detection. [4] N reflects the subjects whose ctDNA doubled.

[5] N reflects subjects whose ctDNA was undetectable or decreased post-baseline.

[REPEAT univariate statistics For VAF + MTM/ML by Assay]

Notes for programming: Timepoints –

- Visits 2, 3 (pre-vaccination)
- Visits 6, 11, 12, 16, 17, 18, 19, 20, 21, 22, 23, 24 (post-vaccination)

Elicio Therapeutics, Inc.  
Protocol ELI-002-001

Confidential

[figure not shown]
Page 1 of x

Figure 1

Ex vivo Fluorospot

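### The SAP addendum defines ctDNA doubling time as a gap between visits, ignoring the size of the rise, and the listing note measures from a nadir that the text does not name

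*SAP*

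**What the plan says.** Addendum section 2.2 (ctDNA) gives the rule: "Doubling will be calculated as the number of weeks between visits where ctDNA first doubles". It supplies no growth-rate formula and does not say which earlier value the doubling is measured against. It applies the rule to both reporting scales, mean tumor molecules per mL and variant allele frequency.

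The Table 7 shell has a *Doubling Time* row with mean, SD, median, minimum and maximum by cohort. Its footnote 4 sets the denominator: "N reflects the subjects whose ctDNA doubled".

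Note 3 to the ctDNA listing (Listing 7) defines the quantity differently: "Doubling time is the time until the ctDNA has increase 2-fold from nadir". It names nadir as the reference but does not say when the clock starts.

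Addendum section 1.6 fixes the baseline: "For ctDNA, this will be the sample collected at Visit 3", with Visit 2 as the fallback. Addendum Table 1-1 places ctDNA samples at Weeks 0, 3, 17, 20, 25, 29, 37, 49, 61, 73, 85, 97 and 105, besides the screening sample. Neither the protocol nor the main SAP text defines doubling time. SAP section 14.0 refers ctDNA analyses to the addendum.

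**The concern.** A doubling time is a rate: the time a quantity takes to double. It depends on both the elapsed time and the size of the change. The addendum's rule uses the size of the change only to decide whether a doubling has occurred, and then reports the elapsed time alone. A subject whose ctDNA rises 16-fold over an interval and one whose ctDNA rises 4-fold over the same interval receive the same value.

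Two consequences follow. The tabulated figure carries the name of a growth rate but takes its possible values from the sampling schedule. And because the text and the listing note use different references, two programmers could follow the addendum faithfully and produce different numbers for the same subject.

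**Working it through.** The documents give no numerical doubling time to reproduce, so the check covers the schedule and how the rule behaves on it.

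**1. Visit grid.** Week = (protocol day − 57)/7, since Visit 3 is Day 57. Visit 6 (Day 78) gives 3.0, Visit 11 (Day 176) 17.0, Visit 12 (Day 196) 19.9, Visit 16 (Day 231) 24.9, Visit 17 (Day 259) 28.9, Visit 18 (Day 315) 36.9 and Visit 19 (Day 399) 48.9, followed by 12-week steps. These agree with Table 1-1 except at Visit 24: Day 819 gives (819 − 57)/7 = 108.9, while the table prints 105. The gaps in Table 1-1 are 3, 14, 3, 5, 4, 8, 12, 12, 12, 12, 12 and 8 weeks. The range is 3 to 14 weeks whichever week is right for Visit 24.

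**2. Direction of the error.** Under exponential growth, values C1 and C2 taken an interval Δt apart give Td = Δt × ln 2 / ln(C2/C1). If C2/C1 ≥ 2, then ln(C2/C1) ≥ ln 2, so Td ≤ Δt. Reporting Δt therefore equals Td when the rise is exactly two-fold and exceeds it otherwise.

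**3. Steady growth from Week 0, rule read as adjacent visits.**

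| True Td (weeks) | Rise by Week 3, 2^(3/Td) | Rise Week 3 to 17, 2^(14/Td) | Reported (weeks) |
|---|---|---|---|
| 2 | 2.83 | not needed | 3 |
| 3.5 | 1.81 | 16 | 14 |
| 7 | 1.35 | 4 | 14 |
| 14 | 1.16 | 2 | 14 |

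At 3.5 and 7 weeks ctDNA has not doubled by Week 3, so the first doubling is seen across the 14-week gap. The overstatement is 14/3.5 = 4-fold and 14/7 = 2-fold. The formula in step 2 recovers the true values: 14 × ln 2 / ln 16 = 3.5 and 14 × ln 2 / ln 4 = 7.0. Read as weeks from baseline, the rule reports 3 + 14 = 17 weeks for both.

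**4. Same interval, different rises.** Over a 12-week follow-up gap, rises of 2-, 4-, 8- and 16-fold correspond to true doubling times of 12, 6, 4 and 3 weeks. The rule returns 12 each time.

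**5. Text against listing note.** Take a baseline of 10, a fall to a nadir of 2 at Week 20, then regrowth with Td = 12 weeks. Values are 2.67 at Week 25, 3.36 at Week 29, 5.34 at Week 37, 10.68 at Week 49 and 21.36 at Week 61.

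- Adjacent visits: the first two-fold step is Week 37 to 49, giving 12 weeks.
- From nadir: the first value of at least 4 is at Week 37, giving 37 − 20 = 17 weeks.
- From baseline: the first value of at least 20 is at Week 61, giving 61 weeks.

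The formula applied from nadir to Week 37 gives 17 × ln 2 / ln(5.34/2) = 12 weeks.

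**The case against.** The strongest reply is that this is a minor descriptive output. Doubling time is not among the objectives or endpoints of the protocol or SAP, no test is attached, and about 18 subjects were planned. Section 2.2 itself describes the listed item as the time until ctDNA doubles, which is an observed time, and any event seen only at visits must fall on the visit grid. Table 7 also gives fold change by visit, and Listing 7 gives dates, values and fold changes, so the size of each rise can be recovered. All of this stands. It limits the importance of the point, but the Table 7 row is still labelled as a doubling time and computed as something else.

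It can also be said that the text names no reference and the note supplies one, so the two may be read together. That is possible, but the text speaks of weeks between visits, and the readings diverge in step 5.

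Several stronger readings are tempting but not supported:

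- **That the value says nothing about growth.** In step 3 a 2-week doubling reports 3 weeks and a 7-week doubling reports 14, so coarse, interval-censored information remains.
- **That a 2-week doubling is reported as 14 weeks, a 7-fold overstatement.** This needs growth to begin at Week 3, for example after a nadir there. With steady growth from Week 0 it reports 3 weeks. Reporting a 3-week doubling as 12 weeks likewise needs growth to start at the opening of a 12-week gap.
- **That Listing 7's fold change from the previous sample is a third doubling time.** It is a fold change with a flag for two-fold steps.
- **That the rule harms a planned pairing of ctDNA with T-cell results.** The stated objective correlates biomarker data with safety, RFS and OS.

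**Conclusion.** The rule is wrong as written for a quantity labelled doubling time. On the nominal schedule it can return only a visit gap or a sum of gaps. Visit windows of ±3 days move the 14-week gap only between 13.1 and 14.9 weeks, and unscheduled samples do not alter the principle. For each subject who doubles, the value equals or overstates the true doubling time, by 4-fold and 2-fold in the steady-growth examples at 3.5 and 7 weeks. Those figures assume noise-free exponential growth.

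A reader might infer that the cohort mean is therefore biased upward. The documents do not establish that: subjects who never doubled are left out of the summary, which pulls the other way, so the net direction is unknown.

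The text and listing note need one reference. The consequence is confined to a descriptive table and listing and touches no endpoint or decision rule.

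**What to change.** Use one definition in addendum section 2.2, Table 7 and the ctDNA listing:

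- Doubling time = interval in weeks, from actual sample dates, × ln 2 / ln(later value / earlier value).
- The earlier value is the nadir sample, or the first detectable sample after an undetectable nadir. The later value is the first subsequent sample at least twice the earlier one.
- Write the criterion as a ratio. Main SAP Table 8 defines fold change as the difference divided by baseline, under which a 2-fold change would be a tripling.
- Beside the summary, report the number who never doubled and the number for whom the value cannot be calculated.

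If the sponsor prefers the observed time, label it *time to first observed doubling from nadir* and treat non-doublers as censored.

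The cost is one formula in the addendum and its programs, using values and dates already collected. The downsides are that reported doubling times become shorter and that a two-point estimate is noisy at low ctDNA levels. An extra ctDNA sample at Visit 9 to split the 14-week gap is not a realistic remedy: last enrolment was planned for 2Q2023, and this is a final-analysis SAP written after long-term follow-up was ended early.

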## **4. CLINICAL STUDY REPORT APPENDICES**

### **4.1. Statistical Tables and Figures to be Generated**

Table 1	Summary and Change from Baseline for ex Vivo Fluorospot
Table 2	Summary and Change from Baseline for In vitro stimulated (IVS) Fluorospot
Table 3	Summary and Change from Baseline for Ex Vivo Intracellular cytokine staining
Table 4 staining	Summary and Change from Baseline In Vitro stimulated Intracellular cytokine
Table 5	Summary and Change from Baseline for Ex Vivo Dextramer
Table 6	Summary and Change from Baseline for In Vitro stimulated Dextramer
Table 7	Summary and Change from Baseline for ctDNA (ctDNA Population)
Figure 1	Scatter and Box Plot of ex Vivo Fluorospot by Cohort Over Time
Figure 2	Scatter and Box Plot of In Vitro Stimulated Fluorospot by Cohort Over Time
Figure 3	Scatter and Box Plot of Ex Vivo Intracellular cytokine staining by Cohort Over Time
Figure 4	Scatter and Box Plot of In Vitro Stimulated Intracellular cytokine staining by Cohort Over Time
Figure 5	Scatter and Box Plot of ex Vivo Dextramer by Cohort Over Time
Figure 6	Scatter and Box Plot of In Vitro Stimulated Dextramer by Cohort Over Time

